4.6 Justification for Exclusion of Women and Children (Special Populations)

4.6.1 Exclusion of Women

- **Pregnancy:** Pregnant women are excluded from this study because there are known adverse effects of ATV, a pregnancy category X drug, on the developing human fetus.

ASA has been listed as a pregnancy category D drug by the FDA due to the potential for known teratogenic or abortifacient effects on the developing fetus.

- **Breast-feeding:** Because there is an unknown but potential risk for adverse events (AEs) in nursing infants secondary to treatment of the mother with ATV, breastfeeding should be discontinued if the mother will be treated with ATV. There is a known risk for AEs in nursing infants secondary to treatment of the mother with ASA, therefore breastfeeding should be discontinued if the mother will be treated with ASA.

4.6.2 Exclusion of Children

Because there are insufficient data regarding dosing or AEs available in HIV-infected adults to judge the potential risk in HIV-infected children, children are excluded from this study.

5 STUDY AGENT/INTERVENTIONS

5.1 Disposition and Dispensation

Study agents will be distributed via the NIH Central Pharmacy according to standard pharmacy procedures.

5.1.1 Formulation, Packaging, and Labeling

Each bottle will be individually labeled with the participant ID number, dosing instructions, recommended storage conditions, the name and address of the manufacturer, randomization number, and that the agent should be kept out of reach of children.

5.2 Study Agent Storage and Stability

Both ATV and ASA should be stored at room temperature, 20-25°C (68-77°F).

5.3 Preparation, Administration, and Dosage of Study Agent/Intervention(s)

5.3.1 Study Agent : atorvastatin

Description

Dosing and Administration: 40 mg tablet, daily. In subjects on certain antiretroviral medications, ATV dosing will be adjusted in accordance with DHHS guidelines [84]. See Table 1 below for list of antiretroviral agents requiring adjustment. Briefly, in subjects on cobicistat -or ritonavir- boosted protease inhibitor or elvitegravir-based regimens, the atorvastatin AUC can increase by 3-6 fold [87]. In subjects on protease inhibitor (other than tipranavir) or elvitegravir-based regimens, the atorvastatin dose will be decreased to 20mg daily. In subjects on efavirenz or etravirine-based regimens, atorvastatin AUC can decrease from 32 to 43%. Therefore, in subjects on efavirenz or etravirine-based regimens, the dose of atorvastatin will be increased to 80mg daily. Dosing of ATV with other ART regimens will also be made in accordance with DHHS guidelines [84].

Table 1. Atorvastatin Interactions with Selected Antiretrovirals and Dosing Recommendations

Antiretroviral Medication	Effect on Atorvastatin	Adjusted Atorvastatin
Atazanavir, Atazanavir with Ritonavir or Cobicistat	Increased Atorvastatin possible	20mg,daily
Darunavir with Ritonavir or Cobicistat	DRV/r + Atorvastatin 10mg similar to Atorvastatin 40mg administered alone	20mg daily
Elvitegravir with Cobicistat (or Ritonavir)	Increased Atorvastatin possible	20mg, daily
Lopinavir with ritonavir	Increased AtorvastatinAUC 488%	20mg daily
Efavirenz, Etravirine	Decreased Atorvastatin AUC 32-43%	80mg daily
Rilpivirine	Atorvastatin AUC unchanged	40mg daily

Route of Administration: PO

Duration of Therapy: 9 months

Tracking of Dose: pill count and participant stated compliance.

Limitations on Prior Therapy: Prior statin therapy allowable if therapy ceased at least 6 months prior to the screening visit.

Subject Access to Study Agent at Study Closure: ATV is only available by prescription, and subjects will be counseled to consult with their primary physician before considering chronic therapy.

5.3.2 Study Agent: aspirin

Description

Dosing and Administration: 81 mg tablet, daily

Route of Administration: PO

Duration of Therapy: 9 months

Tracking of Dose: pill count and participant stated compliance.

Limitations on Prior Therapy: Prior chronic aspirin use allowable if therapy ceased at least 6 months prior to the screening visit.

Use of Ancillary Medications/OTC Products/Foods: Use of systemic corticosteroids, daily NSAID use or immunomodulating medications prohibited at the discretion of the principal investigator (PI)

Subject Access to Study Agent at Study Closure: While ASA is available over-the-counter, subjects will be counseled to consult with their primary physician before considering chronic ASA therapy.

5.4 Study Product Accountability Procedures

We will follow the NIH Central Pharmacy study product accountability procedures.

5.5 Assessment of Subject Compliance with Study Agent/Intervention(s)

Participants will be asked about missing pills at each visit and a pill count will be performed.

5.6 Concomitant Medications and Procedures

All concomitant prescription medications taken during study participation will be documented in the Clinical Research Information Management System of NIAID (CRIMSON). For this protocol, a prescription medication is defined as a medication that can be prescribed only by a properly authorized/licensed clinician. Medications to be reported in CRIMSON are concomitant prescription medications, over-the-counter medications and non-prescription medications taken at the time of AEs (all grades except grade 1).

5.7 Prohibited Medications and Procedures

Treatment with immunomodulating agents, systemic corticosteroids and daily NSAIDs will not be permitted unless discussed with and approved by the study investigator. Subjects treated with a statin or ASA daily up to 6 months prior to the screening visit will also be excluded. Treatment with tipranavir will be prohibited because ATV is contraindicated in these patients. Treatment with any ART regimen combining a non-nucleoside reverse transcriptase inhibitor with a protease inhibitor will be prohibited because of the lack of data concerning drug interactions with ATV.

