8 POTENTIAL RISKS AND BENEFITS

8.1 Potential Risks

Atorvastatin:

Per the package insert (Appendix D), the following warnings and precautions should be considered:

- **Skeletal Muscle Effects:** Rare cases of rhabdomyolysis with acute renal failure secondary to myoglobinuria have been reported with atorvastatin calcium tablets and with other drugs in this class. Atorvastatin, like other statins, occasionally causes myopathy, defined as muscle aches or weakness in conjunction with increases in CPK values >10 times ULN. The concomitant use of higher doses of atorvastatin with certain drugs such as cyclosporine and strong CYP3A4 inhibitors (e.g. clarithromycin, itraconazole, and HIV protease inhibitors) increases the risk of myopathy/rhabdomyolysis.
- **Liver Dysfunction:** Persistent elevations (<3 time ULN occurring on 2 or more occasions in serum transaminases occurred in 0.7% of patients who received atorvastatin calcium tablets in clinical trials.
- **Endocrine Effects:** "Increases in HbA1c and fasting serum glucose levels have been reported with HMG-CoA reductase inhibitors," including ATV.

Aspirin:

According to the ASA package insert (Appendix E), the following warnings and precautions should be considered in patients with the following morbidities:

- **Alcohol Warning:** Increased bleeding risks may occur in patients who consume 3 or more alcoholic drinks a day.
- **Coagulation Abnormalities:** “Even low doses of ASA can inhibit platelet function leading to an increase in bleeding time. This can adversely affect patients with inherited (hemophilia) or acquired (liver disease or vitamin K deficiency) bleeding disorders.”
- **GI Side Effects:** “GI side effects include stomach pain, heartburn, nausea, vomiting, and gross GI bleeding.”
- **Peptic Ulcer Disease:** ASA can cause gastric mucosal irritation and bleeding so patients with a history of active peptic ulcer disease should avoid use.
- **Renal Failure:** Patients with glomerular filtration rates less than 10 mL/minute should avoid use.
- **Hepatic Insufficiency:** Avoid use in patients with hepatic insufficiency.
- **Sodium Restricted Diet:** The high sodium content in buffered ASA preparations should be avoided in patients with sodium retaining states (ie congestive heart failure or renal failure).

Phlebotomy

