11.8 Modification of Study Agent(s)/Intervention(s) for a Subject

If a participant is unable to tolerate ATV or ASA, they will discontinue study drug and will be withdrawn from study. No dose adjustment will occur during the course of this study. See 11.7 for AEs.

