2.5 Dosage in Patients With Renal Impairment

Renal disease does not affect the plasma concentrations nor LDL-C reduction of atorvastatin calcium tablets; thus, dosage adjustment in patients with renal dysfunction is not necessary [see *Warnings and Precautions, Skeletal Muscle (5.1), Clinical Pharmacology, Pharmacokinetics (12.3)*].

2.6 Dosage in Patients Taking Cyclosporine, Clarithromycin, Itraconazole, or Certain Protease Inhibitors

In patients taking cyclosporine or the HIV protease inhibitors (tipranavir plus ritonavir) or the hepatitis C protease inhibitor (telaprevir), therapy with atorvastatin calcium tablets should be avoided. In patients with HIV taking lopinavir plus ritonavir, caution should be used when prescribing atorvastatin calcium tablets and the lowest dose necessary employed. In patients taking clarithromycin, itraconazole, or in patients with HIV taking a combination of saquinavir plus ritonavir, darunavir plus ritonavir, fosamprenavir, or fosamprenavir plus ritonavir, therapy with atorvastatin calcium tablets should be limited to 20 mg, and appropriate clinical assessment is recommended to ensure that the lowest dose necessary of atorvastatin calcium tablets is employed. In patients taking the HIV protease inhibitor nelfinavir or the hepatitis C protease inhibitor boceprevir, therapy with atorvastatin calcium tablets should be limited to 40 mg, and appropriate clinical assessment is recommended to ensure that the lowest dose necessary of atorvastatin calcium tablets is employed [see *Warnings and Precautions, Skeletal Muscle (5.1), Drug Interactions (7)*].

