7 DRUG INTERACTIONS

The risk of myopathy during treatment with statins is increased with concurrent administration of fibric acid derivatives, lipid-modifying doses of niacin, cyclosporine, or strong CYP 3A4 inhibitors (e.g., clarithromycin, HIV protease inhibitors, and itraconazole) [see *Warnings and Precautions, Skeletal Muscle* (5.1) and *Clinical Pharmacology* (12.3)].

7.1 Strong Inhibitors of CYP 3A4: Atorvastatin is metabolized by cytochrome P450 3A4. Concomitant administration of atorvastatin calcium tablets with strong inhibitors of CYP 3A4 can lead to increases in plasma concentrations of atorvastatin. The extent of interaction and potentiation of effects depend on the variability of effect on CYP 3A4.

Clarithromycin: Atorvastatin AUC was significantly increased with concomitant administration of atorvastatin calcium tablets 80 mg with clarithromycin (500 mg twice daily) compared to that of atorvastatin calcium tablets alone [see *Clinical Pharmacology* (12.3)]. Therefore, in patients taking clarithromycin, caution should be used when the atorvastatin dose exceeds 20 mg [see *Warnings and Precautions, Skeletal Muscle* (5.1) and *Dosage and Administration* (2.6)].

Combination of Protease Inhibitors: Atorvastatin AUC was significantly increased with concomitant administration of atorvastatin calcium tablets with several combinations of HIV protease inhibitors, as well as with the hepatitis C protease inhibitor telaprevir, compared to that of atorvastatin calcium tablets alone [see *Clinical Pharmacology* (12.3)]. Therefore, in patients taking the HIV protease inhibitor tipranavir plus ritonavir, or the hepatitis C protease inhibitor telaprevir, concomitant use of atorvastatin calcium tablets should be avoided. In patients taking the HIV protease inhibitor lopinavir plus ritonavir, caution should be used when prescribing atorvastatin calcium tablets and the lowest dose necessary should be used. In patients taking the HIV protease inhibitors saquinavir plus ritonavir, darunavir plus ritonavir, fosamprenavir, or fosamprenavir plus ritonavir, the dose of atorvastatin calcium tablets should not exceed 20 mg and should be used with caution [see *Warnings and Precautions, Skeletal Muscle* (5.1) and *Dosage and Administration* (2.6)]. In patients taking the HIV protease inhibitor nelfinavir or the hepatitis C protease inhibitor boceprevir, the dose of atorvastatin calcium tablets should not exceed 40 mg and close clinical monitoring is recommended.

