Itraconazole: Atorvastatin AUC was significantly increased with concomitant administration of atorvastatin calcium tablets 40 mg and itraconazole 200 mg [see *Clinical Pharmacology* (12.3)]. Therefore, in patients taking itraconazole, caution should be used when the atorvastatin dose exceeds 20 mg [see *Warnings and Precautions, Skeletal Muscle* (5.1) and *Dosage and Administration* (2.6)].

7.2 Grapefruit Juice: Contains one or more components that inhibit CYP 3A4 and can increase plasma concentrations of atorvastatin, especially with excessive grapefruit juice consumption (>1.2 liters per day).

7.3 Cyclosporine: Atorvastatin and atorvastatin-metabolites are substrates of the OATP1B1 transporter. Inhibitors of the OATP1B1 (e.g., cyclosporine) can increase the bioavailability of atorvastatin. Atorvastatin AUC was significantly increased with concomitant administration of atorvastatin calcium tablets 10 mg and cyclosporine 5.2 mg/kg/day compared to that of atorvastatin calcium tablets alone [see *Clinical Pharmacology* (12.3)]. The co-administration of atorvastatin calcium tablets with cyclosporine should be avoided [see *Warnings and Precautions, Skeletal Muscle* (5.1)].

7.4 Gemfibrozil: Due to an increased risk of myopathy/rhabdomyolysis when HMG-CoA reductase inhibitors are co-administered with gemfibrozil, concomitant administration of atorvastatin calcium tablets with gemfibrozil should be avoided [see *Warnings and Precautions* (5.1)].

7.5 Other Fibrates: Because it is known that the risk of myopathy during treatment with HMG-CoA reductase inhibitors is increased with concurrent administration of other fibrates, atorvastatin calcium tablets should be administered with caution when used concomitantly with other fibrates [see *Warnings and Precautions* (5.1)].

7.6 Niacin: The risk of skeletal muscle effects may be enhanced when atorvastatin calcium tablets are used in combination with niacin; a reduction in atorvastatin calcium tablets dosage should be considered in this setting [see *Warnings and Precautions* (5.1)].

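### Apart from antiretrovirals, the plan has no rule for drugs that interact with atorvastatin: 40 or 80 mg may be taken with clarithromycin or itraconazole against a 20 mg label limit, and gemfibrozil is not barred

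*Combined protocol and SAP*

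**What the plan says.** Section 5.3.1 sets the ATV dose and its only trigger for adjustment: "40 mg tablet, daily. In subjects on certain antiretroviral medications, ATV dosing will be adjusted in accordance with DHHS guidelines". Protease-inhibitor (other than tipranavir) and elvitegravir regimens go down to 20 mg. For efavirenz or etravirine, "the dose of atorvastatin will be increased to 80mg daily". The closing catch-all in that section covers other ART regimens only.

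Section 5.7 contains two prohibitions based on ATV interactions. One is "Treatment with tipranavir will be prohibited because ATV is contraindicated in these patients"; the other covers regimens that combine an NNRTI with a protease inhibitor. It also restricts immunomodulators, systemic corticosteroids and daily NSAIDs, and section 11.10 repeats those three classes as reasons to stop drug. Section 5.6 provides for concomitant drugs to be recorded and attaches no action.

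Section 11.8 adds: "No dose adjustment will occur during the course of this study".

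Section 8.1 warns that higher ATV doses taken with "strong CYP3A4 inhibitors (e.g. clarithromycin, itraconazole, and HIV protease inhibitors) increases the risk of myopathy/rhabdomyolysis", but gives no dose limit, hold or prohibition. Gemfibrozil is not named in the protocol body.

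The ATV label is Appendix D. For clarithromycin or itraconazole, its section 2.6 says "therapy with atorvastatin calcium tablets should be limited to 20 mg", and Table 1 in label section 5.1 repeats that limit. Label section 7.1 is milder: "caution should be used when the atorvastatin dose exceeds 20 mg". On gemfibrozil, label section 7.4 says "concomitant administration of atorvastatin calcium tablets with gemfibrozil should be avoided".

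**The concern.** The protocol follows its appended label for antiretrovirals but not for other drugs that the label treats in the same way. Clarithromycin and itraconazole are ordinary prescriptions that a participant could receive from an outside doctor during nine months of treatment. If that happens, an investigator who follows the protocol has no instruction to act, and one who follows the label by reducing ATV to 20 mg departs from section 11.8.

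What is at stake is avoidable myopathy or rhabdomyolysis in people whom section 8.2 promises no direct benefit and who, according to the protocol summary, have no clinical indication for the drug. Treatment visits fall at Months 3, 6, 9 and 12, so a short antibiotic or antifungal course can begin and end before the next medication history or creatine kinase test.

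**Working it through.** The plan gives no figure to reproduce. The check sets the protocol's rules beside the label's and then compares doses.

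**Label against protocol**

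| Co-administered drug | Label (Appendix D) | Label AUC change (Table 3) | Protocol rule |
|---|---|---|---|
| Tipranavir/ritonavir | Avoid ATV (Table 1) | 9.4-fold | Prohibited (5.7) |
| Darunavir/ritonavir | At most 20 mg (2.6, Table 1) | 3.4-fold | 20 mg (5.3.1) |
| Clarithromycin | At most 20 mg (2.6, Table 1); caution above 20 mg (7.1) | 4.4-fold | None; warning only in 8.1 |
| Itraconazole | At most 20 mg (2.6, Table 1); caution above 20 mg (7.1) | 3.3-fold | None; warning only in 8.1 |
| Gemfibrozil | Avoid (7.4) | Up 35% | None; not named |

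Clarithromycin and itraconazole share a row of label Table 1 with darunavir/ritonavir, and their effects on ATV exposure are of similar or greater size. The protocol manages one of the three.

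**Dose against the 20 mg limit (clarithromycin or itraconazole)**

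- Default dose, which covers elite controllers (no ART) and rilpivirine regimens: 40 / 20 = 2 times.
- Efavirenz or etravirine regimens, nominal: 80 / 20 = 4 times.
- The 80 mg dose offsets an AUC fall of 32 to 43% (section 5.3.1). If AUC is proportional to dose and the fall persists, the equivalent dose is 80 × (1 − 0.43) = 45.6 mg to 80 × (1 − 0.32) = 54.4 mg. Then 45.6 / 20 = 2.28 and 54.4 / 20 = 2.72, or about 2.3 to 2.7 times.
- Participants on boosted protease-inhibitor, atazanavir or elvitegravir regimens already take 20 mg and are at the limit, not above it.

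**Illustration of exposure**, again assuming AUC proportional to dose:

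- 40 mg with clarithromycin: 40 × 4.4 = 176 mg-equivalent. At 20 mg: 20 × 4.4 = 88.
- 40 mg with itraconazole: 40 × 3.3 = 132 mg-equivalent. At 20 mg: 20 × 3.3 = 66.

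At the protocol's default dose both figures exceed the label's 80 mg maximum. No dose ratio applies to gemfibrozil, because the label says to avoid the combination on grounds of myopathy risk.

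**Whether other text closes the gap**

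- Exclusion 3 in section 4.5 covers other contraindications to statin therapy, but its examples are diseases. The label's own contraindications (4.1 to 4.4) list none of the three drugs.
- Exclusion 1 uses an LDL threshold of 190 mg/dL, so it does not remove someone taking gemfibrozil for triglycerides.
- Under section 11.10, developing an exclusion on study only may lead to discontinuation.
- Section 11.10 also requires discontinuation when continuing is not in the subject's best interest, but that is a case-by-case judgement.
- Creatine kinase, aldolase and liver tests are done at every visit. They detect harm rather than prevent it, and visits are three months apart.

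**The case against.** The strongest reply is that the plan permits these combinations only by silence. No sentence authorises them, the label is part of the protocol, and section 8.1 says its warnings should be considered. The no-adjustment sentence in 11.8 follows one about intolerance, so it may have been meant for that setting; even read broadly, it leaves discontinuation open. Gemfibrozil at entry may already be excluded: section 5.7 calls ATV contraindicated with tipranavir where the label says only to avoid it, and on that usage exclusion 3 would reach gemfibrozil too. The label is also not uniform on fibrates: its sections 2.4 and 5.1 advise caution and weighing of risk, and only 7.4 is categorical.

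Some of this stands. The combinations are tolerated, not directed; a route to stopping drug exists; and the case on gemfibrozil at entry is weaker than the case on study. The 2.3 to 2.7 figure assumes that the efavirenz or etravirine effect persists alongside a strong CYP3A4 inhibitor, which no text supports. It is also a dose ratio, not a risk.

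The gap remains nonetheless. The wording of 11.8 is unqualified, label 2.6 and Table 1 state the 20 mg limit outright, and none of the general provisions names a drug or requires an action. The label's list is longer than three drugs. Telaprevir, also under avoid in Table 1, is largely moot because exclusion 9 bars chronic hepatitis C. Erythromycin, niacin and colchicine carry cautions without a fixed ATV limit.

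**Conclusion.** The concern holds. If sections 5.3.1, 5.7 and 11.8 are followed as written, ATV can be given at 2 times the appended label's limit with clarithromycin or itraconazole. On efavirenz or etravirine the ratio is nominally 4 times, or about 2.3 to 2.7 times if AUC is proportional to dose and the induction effect persists. ATV can also be given with gemfibrozil, which the label says to avoid. Section 11.8 additionally stands in the way of the label's reduction to 20 mg.

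This should be corrected on grounds of individual safety in the ATV arm. The documents do not say how many participants would be affected, and no effect on the sCD14 endpoint or on the toxicity comparison is claimed. The consent pages and the pharmacy procedures were not available, so advice to participants or dispensing checks may exist there.

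**What to change.** 1. **Section 5.7:** add gemfibrozil to the prohibited drugs. Check for it at screening and again at Month 3 before randomisation, so that eligibility is the same for both arms.
2. **Section 5.3.1:** require ATV to be held, or limited to 20 mg or less, for as long as clarithromycin or itraconazole is taken. For anyone already on 20 mg with a boosted protease inhibitor, a hold is the better choice, because the limit alone would change nothing.
3. **Section 11.8:** add a matching exception, so that this hold or reduction is not a protocol deviation.
4. **Every visit:** ask about the three drugs as part of the medication history already taken. Unless the consent form already does so, tell participants at Month 3 to call before starting any of them.

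The cost is one amendment to 5.3.1, 5.7 and 11.8, with no new visit or test. A few candidates may be deferred or excluded, and some ATV participants will have short holds or dose reductions.

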6 STUDY SCHEDULE

For the purposes of this study, a month is a calendar month. A window of up to ± 2 weeks will be acceptable for all visits after the baseline visit. Visits that include procedures (MRI or pheresis) may be completed in more than one day.

